For analyses relating to the primary objective, group comparisons will be performed using a repeated measures mixed model, adjusted for baseline factors and with treatment as the main effect. Prior to analysis, all endpoints will be assessed for conformance to normality assumptions and the appropriate transformation will be conducted if necessary. Some exploratory endpoints may only be available in the active treatment group. In this case, a within group analysis will be conducted to compare baseline and post-baseline measurements.

An interim analysis will be conducted when 12 participants have been randomised. The results of the interim analysis will be used to re-estimate the sample size if necessary.

3 Background and rationale

Clinical background

COVID-19 is a heterogeneous disease caused by infection with SARS-CoV-2 and although the majority of patients (80%) have mild disease, 15% will require oxygen and of these 25% will require ICU, of which 47 – 71% require ventilatory support. Risk factors for severe disease include older age, male sex, obesity and comorbid disease. There are no specific cures for COVID-19 and current care is supportive. A key challenge is to intercept patients early in the course of their disease to prevent deterioration and reduce the numbers that need ventilatory support, a life-saving treatment that is currently only available for a minority of patients.

SARS-CoV-2 is able to directly infect nasal, bronchiolar and alveolar epithelial cells resulting in lung inflammation, characterised, in severe cases, by an over-exuberant inflammatory response, shortness of breath and hypoxaemia. Once SARS-CoV-2 infection progresses to the stage of pneumonia, key pathogenic drivers result in symptoms characteristic of the acute respiratory distress syndrome (ARDS) with a high mortality.

In patients with confirmed COVID-19 pneumonia, 50% developed dyspnoea at 8 days after illness onset (range: 5–13 days). Mortality of these patients is around 4-15%, as a result of ARDS, coagulation dysfunction, and secondary infection that may result in septic shock and multi-organ failure (Zhou et al., Lancet 2020). Cytokines are thought to be key drivers of these pathological events and in particular levels of IL-6 are found to be raised in COVID-19 patients and to correlate with mortality (Gong et al., medRxiv 2020). Anti-IL-6 is seen as a potential therapy in COVID-19 following favourable reports from a clinical study in China.

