Due to the evolving situation with hospitalised COVID-19 participants, the burden on the NHS and the availability of other COVID-19 trials, it is considered inappropriate to conduct a placebocontrolled study. Therefore, a randomised, controlled, open-label approach where dornase alfa is administered on top of BAC and compared to BAC alone has been adopted.

The data derived from the 10 participants who are randomised to the BAC arm of the study who do not receive dornase alfa will provide control data for all of the study endpoints.

The 30 participants randomized to BAC + dornase alfa will be compared to 10 randomised controls from the COVASE study. In addition, 10 participants in other clinical trials on BAC (biobanked samples) and 60 participants from a historic database of the first 120 people with COVID-19 treated at UCLH will also be used as comparator data.

However, to enhance the control group, a hybrid approach will be applied such that additional data will be combined with the randomised controls, illustrated in Figure 3. The sample size calculation indicates that 90 evaluable participants are required (60 control:30 active). These control data may include: data from the randomised BAC arm, historic COVID-19 UCLH database, biobanked samples from other ongoing trials and observational trials in COVID-19.

This hybrid strategy allows two things:

- provides comparators for all of the study objectives (including limited data for the exploratory objectives)
- demonstrates that the historic controls are representative/similar to the study population

Comparator data from UCLH is available as historic controls for the Primary and Secondary Endpoints. A database of the first 120 participants with COVID-19 admitted to UCLH is available and being analysed currently. CRP is routinely measured daily (or on alternate days) in all participants admitted to UCLH and will be used to control for the Primary Endpoint. All of the Secondary Endpoints are also routinely measured and will be available in the database. Participants in the database will be selected to act as controls as follows:

- 1. Apply the inclusion and exclusion criteria of the COVASE study
- 2. Additional selection to identify closest matches using a propensity score based on age, gender, BMI, baseline CRP, oxygen requirements and the number of comorbidities.

At least 60 control participants are expected to be available to act as controls.

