- Ventilator-associated pneumonia (VAP) or hospital-acquired pneumonia

• Survival (days)

In participants who are discharged before Day35, a telephone call will occur at Day35 to ask them about their breathing e.g. Are you short of breath? Has your breathing returned to the same level as previously?

A schedule of all trial assessments and procedures is set out in Appendix 1.

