11.3.3 Secondary outcome analysis

This study was not powered to detect any effects relating to secondary endpoints. Therefore, the secondary analysis will involve descriptive statistics. In general, continuous data will be summarised using the mean (standard deviation), median (1st and 3rd quartiles), minimum and maximum, and categorical data will be represented as frequency counts (percentages).

A further comparison of the secondary endpoints will involve the appropriate general linear models for binary, continuous or ordinal data with age, gender, BMI, baseline value, oxygen requirements and the number of comorbidities as covariates and treatment as a main effect. This will provide the adjusted means and 95% confidence intervals for the endpoint in the active and control groups. The same model will be used to estimate the difference between the groups and the associated confidence interval.

Continuous endpoints will be assessed for conformance to normality assumptions and the appropriate transformation will be conducted if necessary.

A survival analysis will be conducted on the time to event data. The Kaplan-Meier method will be used to estimate the median survival times and the associated 95% confidence intervals. The time to event data will be censored at 28 days post last dose (Day35) for the randomised participants and at the date of the last electronic record for the historical control group. The survival model will include treatment as a stratification variable. A cox proportional hazards model will be used to generate a hazard ratio and associated confidence intervals, adjusting for age, gender, BMI, baseline value, oxygen requirements and the number of comorbidities as covariates and treatment as a main effect.

The secondary outcome analysis will use the primary analysis population.

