#### 2.2.2 Secondary Endpoints

Secondary endpoints include, but are not limited to:

- Levels of acute phase reactant CRP over 35 days follow-up
- Length of hospitalisation from baseline (days)
- Survival at Day35, mortality data collected from EPIC database for both HCs and randomised individuals
- White blood cell count over 7 days follow-up
- Neutrophil count over 7 days follow-up
- Lymphocyte count over 7 days follow-up
- Monocyte count over 7 days follow-up
- Eosinophil count over 7 days follow-up
- Basophil count over 7 days follow-up
- Procalcitonin over 7 days follow-up
- D-dimer count over 7 days follow-up
- Blood pressure over 7 days follow-up
- Pulse rate over 7 days follow-up
- Temperature over 7 days follow-up
- Respiratory rate over 7 days follow-up
- Time on Oxygen over 7 days follow-up
- Time on Oxygen over 35 days follow-up
- Proportion of individuals with Pneumonia over 7 days follow-up
- Ordinal score (WHO scoring tool) over 7 days follow-up (including randomized individuals only)
- Proportion of individuals on Mechanical Ventilation (MV) over 7 days follow-up
- Time on MV over 7 days follow-up
- Length of ICU stay (hours) over 7 days follow-up
- Proportion of individuals with Pneumonia over 35 days follow-up
- Proportion of individuals on Mechanical Ventilation (MV) over 35 days follow-up
- Time on MV over 35 days follow-up
- Length of ICU stay (hours) over 35 days follow-up

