#### **Exploristics Limited**

### Identifier: EXP20012 Clinical Study Identifier: 132333

reinstating dornase alfa treatment for up to 7 further days (14 days in total). Blood sampling, as specified, will continue until the last day of dosing with dornase alfa.

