For the following secondary endpoints, a survival analysis will be conducted. The number of events by arm will be compared. The time to event data will be censored at 28 days post last dose (Day35) for the randomised participants and at 35 days after baseline, or the date of the last electronic record, whichever is earlier, for the historical control group. If median time-to-event times exist, the Kaplan-Meier method will be used to estimate the median time-to-event times and the associated 95% confidence intervals. The survival model will include treatment as a stratification variable and significance assessed using a log-rank test. A Cox proportional hazards model will be used to generate a hazard ratio and associated confidence intervals, adjusting for age, baseline CRP value (defined as the last CRP measurement prior to randomisation, or the first CRP following Dexamethasone for HCs) and treatment as a main effect. For the time to discharge from hospital analysis, data will be censored if the participant dies prior to discharge at the date of death.

- Survival at Day35
- Time to discharge from hospital from baseline (days) to Day 35

For the following secondary endpoint, a logistic regression model will be fitted, with age, gender, BMI baseline CRP value (defined as the last CRP measurement prior to randomisation, or the first CRP

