## **Exploristics Limited**

Identifier: EXP20012

Clinical Study Identifier: 132333

The secondary outcome analysis will use the primary analysis population.

Note: if models fail to converge or have evidence of over-fitting, covariates will be removed from the models in the following order: serious condition, Sex, Age, BMI, baseline value of measurement.

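### Day-35 survival: historical controls can be censored earlier than randomised patients, at an undefined last record, so the hazard ratio can be biased in a direction the documents do not settle

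*SAP*

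**What the plan says.** SAP 11.2 censors randomised participants at a point it describes as 28 days after the last dose and labels Day 35. Historical controls are censored at 35 days after baseline "or the date of the last electronic record, whichever is earlier, for the historical control group". The same sentence governs survival and time to discharge. A log-rank test and a Cox model adjusted for age and baseline CRP follow.

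Protocol 11.3.3 also splits the rule by data source, but differently: controls are censored "at the date of the last electronic record for the historical control group", with no cap at Day 35.

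Related statements:

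- SAP 2.2.2 names the source of deaths: "Survival at Day35, mortality data collected from EPIC database for both HCs and randomised individuals".
- Protocol 5.1 says of the historical database: "All of the Secondary Endpoints are also routinely measured and will be available in the database".
- Protocol 8.4.1 provides contact after discharge for trial participants: "In participants who are discharged before Day35, a telephone call will occur at Day35 to ask them about their breathing". No counterpart is described for historical controls.
- SAP 11.2 fixes the population: "The secondary outcome analysis will use the primary analysis population". Under SAP 6.1 and 12 that is 30 on dornase alfa against 10 randomised to best available care (BAC) and about 60 matched historical controls.

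Neither document defines the last electronic record, says how many controls have one before Day 35, or plans a sensitivity analysis of the censoring rule.

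**The concern.** Censoring is harmless when it is unrelated to prognosis. A hospital record may stop because the patient recovered and went home. A surviving control with such a record leaves the risk set at discharge, while an equally well randomised survivor stays in it to Day 35. If control deaths are still all counted, the control hazard is inflated and dornase alfa looks better than it is. Age and baseline CRP cannot repair this, because the censoring depends on recovery after baseline.

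The opposite error is also possible. If a control's record stops at discharge and a later death never reaches EPIC, a control event is lost and the comparison moves against dornase alfa. One undefined term therefore leaves open both the size and the sign of the bias in a mortality hazard ratio that readers will notice.

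**Working it through.** The plan gives no figure for survival to reproduce; its sample size of 90 is for CRP only. The check asks what the Cox model estimates when the true hazard ratio is 1.

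**Inputs from the documents.** Group sizes are 30 dornase alfa, 10 BAC and 60 historical (SAP 12). Protocol section 3 says "Mortality of these patients is around 4-15" per cent; 10% is the central case, the same in every group.

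**Assumptions, not in the documents.** Discharge times of survivors are lognormal with median day 8, 10 or 12. Death times are lognormal with median day 7, 10 or 14, restricted to before Day 35. Sigma is 0.6 for both. A quarter, half or all of surviving controls have records that end at discharge. A share of control deaths, 0, 15 or 30%, is missing from EPIC.

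**Formula.** With n₁(t), n₀(t) the expected numbers at risk and e₁(t), e₀(t) the expected deaths on dornase alfa and in the pooled comparator, the large-sample hazard ratio θ solves

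Σₜ { e₁(t) − [e₁(t)+e₀(t)] · n₁(t)θ / [n₁(t)θ + n₀(t)] } = 0.

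**Hand check** (day 10; discharge median 8, death median 10, half of records ending early):

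- Share of survivors not yet discharged: 1 − Φ(ln(10/8)/0.6) = 0.355.
- Share of deaths still to come: 1 − 0.5/Φ(ln(35/10)/0.6) = 0.491.
- At risk per randomised patient: 0.9 + 0.1 × 0.491 = 0.949.
- At risk per historical control: 0.9 × (0.5 + 0.5 × 0.355) + 0.049 = 0.659.
- Dornase alfa at risk: 30 × 0.949 = 28.5. Comparator: 60 × 0.659 + 10 × 0.949 = 49.0.
- Deaths arise in the ratio 30:70, so the hazard ratio that day is (30/28.5)/(70/49.0) = 0.74. The full solution for this case is 0.741.

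**Null hazard ratio, all deaths captured** (range over the nine combinations of median days):

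| Mortality | Quarter end early | Half | All |
|---|---|---|---|
| 4% | 0.84-0.94 | 0.68-0.88 | 0.32-0.73 |
| 10% | 0.85-0.94 | 0.69-0.88 | 0.33-0.73 |
| 15% | 0.85-0.94 | 0.70-0.88 | 0.35-0.74 |

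A separate simulation with gamma-distributed times gave 0.32-0.56 at 4-15% mortality when all control records end at discharge. It gave 0.99 when the record end is unrelated to outcome.

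**Null hazard ratio, control deaths missed, 10% mortality:**

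| Missed | None end early | Quarter | Half |
|---|---|---|---|
| 15% | 1.16 | 0.98-1.09 | 0.80-1.02 |
| 30% | 1.37 | 1.15-1.29 | 0.94-1.20 |

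Expected control deaths in EPIC fall from 60 × 0.10 = 6.0 to 5.1 or 4.2. Early censoring of survivors alone leaves the count at 6.0.

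**Against sampling error.** Expected deaths are 30 × 0.10 = 3 and 70 × 0.10 = 7, so SE(log HR) = √(1/3 + 1/7) = 0.69. A hazard ratio of 0.74 then has a 95% interval of 0.74 × exp(±1.96 × 0.69), about 0.19 to 2.9. With all deaths captured, the simulated chance of a two-sided 5% log-rank result favouring dornase alfa is 1.3-1.4% with no early ending, 1.8-2.7% at a quarter, 2.5-6.0% at half and 5.4-36% if all end early. The nominal value is 2.5%.

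**The Day-35 label.** 7 + 28 = 35 holds only for seven days of dosing. SAP 3 allows "reinstating dornase alfa treatment for up to 7 further days (14 days in total"), and 14 + 28 = 42. BAC patients have no dose from which to count.

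**The case against.** The strongest reply is that the two conditions for a bias towards dornase alfa pull against each other. Records must end at discharge, yet later deaths must still reach EPIC. If EPIC holds later vital status, the last record may run later too; if it does not, deaths are missed and the bias shrinks or reverses. This stands, and it is why no direction can be claimed. A reader might infer that the plan is shown to favour dornase alfa, or might take 0.33 or 36% as its likely consequence. The documents support neither: those extremes need every surviving control's record to stop at discharge with all deaths captured.

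A second reply is that EPIC serves both groups. That settles where deaths come from, not how long a surviving control stays at risk.

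Third, the status of randomised survivors after discharge is not fully secured either. The Day-35 call asks about breathing, no rule covers an unanswered call, and Protocol 5.1, SAP 3 and SAP 4 describe follow-up as ending at discharge. This is fair, and is a reason to reconcile those statements.

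Fourth, SAP 8.4 and 11.2 call secondary analyses descriptive, and SAP 11.2 also compares event counts, which early censoring of survivors alone leaves unchanged. That limits the weight of the point. It does not remove it, because the same section plans a log-rank significance assessment and a hazard ratio with its interval.

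**Conclusion.** The point holds as a defect in the censoring rule. SAP 11.2 applies different rules by data source in one model and leaves the controls' rule undefined; Protocol 11.3.3 states a third version. At 10% mortality and no true effect, plausible partial shares give hazard ratios from about 0.69 (half of control records ending early, deaths complete) to 1.29 (a quarter ending early, 30% of control deaths missed). With complete records and deaths there is no bias. These sizes rest on assumed discharge and death times, shares of early record ends and missed deaths; none of these is in the documents.

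At partial shares sampling error is larger than the bias. The endpoint is secondary and unpowered, and the primary CRP analysis is untouched. The change should be made because it is cheap and the plan offers no way to tell which case applies.

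**What to change.** 1. For survival at Day 35, use one rule in every group: the event is a death recorded in EPIC within 35 days of baseline; everyone else is censored at Day 35 after baseline.
2. Define the last-record date, and pre-specify a sensitivity analysis that censors every group by it.
3. Report by group how many survivors' last record falls before Day 35. The sensitivity analysis cannot be read without this count: its null hazard ratio is 1.00 if equal shares end at discharge, but 0.81-0.94 if half of controls and a quarter of randomised patients do.
4. State that EPIC completeness after discharge may differ between historical and randomised patients.
5. State separately that time to discharge also uses one common censoring rule in all groups.
6. Count randomised censoring from baseline (Day 35 after baseline), not from the last dose, and reconcile Protocol 5.1, Protocol 11.3.3, SAP 3 and SAP 4 with SAP 11.2.

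The cost is a paragraph of SAP text, one repeat of the model, one count table and the wording reconciliation. No new data source is needed. The downside is that deaths missing from EPIC count as alive. If that is more common in historical controls, the Day-35 rule is biased against dornase alfa (about 1.16 or 1.37 with 15% or 30% missed), hence the paired analysis and the stated limitation.

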#### 8.2 Independent Variables

For the primary endpoint analysis, the independent variables included in the model will be treatment (dornase alfa vs. no dornase alfa), age, gender, BMI, baseline CRP level (defined as the last CRP value prior to randomisation, or the first CRP following Dexamethasone for HCs), time from baseline and whether they have a key comorbidity, defined as one or more of hypertension, diabetes or cardiovascular disease. An interaction term between treatment and time from baseline will also be included in the model.

For secondary endpoint analyses, the same covariates will be included in the models as for the primary endpoint analysis.

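### SAP 11.2 adjusts the time-to-discharge Cox model for age and baseline CRP only, although SAP 8.2 promises the primary model's covariates and most comparators are not randomised

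*SAP*

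**What the plan says.** SAP 8.2 sets the primary model's independent variables as "treatment (dornase alfa vs. no dornase alfa), age, gender, BMI, baseline CRP level", time from baseline with its treatment interaction, and "whether they have a key comorbidity, defined as one or more of hypertension, diabetes or cardiovascular disease". It then extends the list: "For secondary endpoint analyses, the same covariates will be included in the models as for the primary endpoint analysis".

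SAP 11.2 gives a single Cox specification, "adjusting for age, baseline CRP value" and treatment, and applies it to two endpoints: survival at Day 35 and "Time to discharge from hospital from baseline (days) to Day 35". For the discharge endpoint, "data will be censored if the participant dies prior to discharge at the date of death". Significance in these time-to-event analyses comes from a log-rank test; the Cox model supplies the hazard ratio and confidence interval.

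The other regressions in SAP 11.2 (repeated measures, logistic and linear) all keep gender, BMI and key comorbidity. One of them is the linear model for length of hospitalisation from baseline. A closing note in 11.2 says that "if models fail to converge or have evidence of over-fitting, covariates will be removed from the models in the following order". The order it gives starts with a serious-condition term and then takes out sex, followed by age, followed by BMI, with the baseline value last.

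Protocol 11.3.3 describes a Cox model "adjusting for age, gender, BMI, baseline value, oxygen requirements and the number of comorbidities as covariates and treatment as a main effect". Protocol 11.1.2 recognises one survival endpoint and classes length of hospital stay as a continuous measure.

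**The concern.** The two SAP sections cannot both be followed. Under 8.2 the Cox model has five covariates plus treatment; under 11.2 it has two plus treatment. No reason is given for the difference, and 8.2 does not record the Cox model as an exception.

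The difference could matter for discharge because the comparison is mostly not randomised. SAP section 12 plans 30 dornase alfa participants, 10 randomised to BAC and 60 historical controls, and the secondary analyses use this population. SAP section 11 matches the historical controls by nearest neighbour on a propensity score, with no caliper or balance criterion stated. At least 60 eligible controls are expected for 60 places, so matching may have little room to choose. Any imbalance left in gender, BMI or comorbidity passes straight into the short model's discharge hazard ratio if those variables affect time to discharge. The log-rank test adjusts for nothing, so the Cox model is the only adjusted time-to-event estimate for discharge.

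**Working it through.** **1. The plan's own figure.** The documents give no event count or power for discharge or survival. Their only sample-size figure is 90 (30:60) for CRP. With a difference of 0.40 × 99 = 39.6 mg/L, SD 62 mg/L and a two-sided 5% t-test (sidedness assumed), 29:58 gives 79.3% power and 30:60 gives 80.7%, so 90 reproduces. It does not bear on discharge beyond fixing the group sizes. The final analysis is planned at 30 + 10 + 60 = 100.

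**2. The covariate lists side by side.**

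| Source | Age | Baseline | Gender | BMI | Comorbidity | Oxygen |
|---|---|---|---|---|---|---|
| SAP 8.2, secondary models | yes | CRP | yes | yes | key, yes/no | no |
| SAP 11.2, Cox | yes | CRP | no | no | no | no |
| SAP 11.2, linear, length of hospitalisation | yes | CRP | yes | yes | key, yes/no | no |
| Protocol 11.3.3, Cox for survival | yes | baseline value | yes | yes | number | yes |

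**3. Could the removal rule have produced the Cox list?** No. The rule acts only after non-convergence or evidence of over-fitting, and it removes age before BMI. The Cox model keeps age and omits BMI. This holds whether or not serious condition in that rule means key comorbidity.

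**4. Do event numbers justify the short list?** Events per parameter = events ÷ parameters, with 3 parameters in the short model and 6 under SAP 8.2. Deaths use the 4–15% mortality in Protocol section 3 on 100 patients. The discharge counts are an assumption; the upper one is 100 − 4 = 96.

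| Events | Per parameter, 3 | Per parameter, 6 |
|---|---|---|
| 4 deaths | 1.3 | 0.7 |
| 15 deaths | 5.0 | 2.5 |
| 50 discharges | 16.7 | 8.3 |
| 60 discharges | 20.0 | 10.0 |
| 85 discharges | 28.3 | 14.2 |
| 96 discharges | 32.0 | 16.0 |

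Few events can explain a short model for survival. For discharge they cannot, provided that about 60% or more are discharged by Day 35.

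**5. Possible size of the bias.** To first order, bias in the log hazard ratio ≈ Σ (log effect of each omitted covariate × imbalance). Effects and imbalances are assumed; the documents give neither.

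- Assumed discharge hazard ratios: 0.6 for comorbidity (log −0.511), 0.82 per SD of BMI (−0.198), 0.8 for sex (−0.223).
- Controls with 20 points more comorbidity, 0.3 SD higher BMI and 10 points more of the slower-discharged sex: 0.2 × 0.511 + 0.3 × 0.198 + 0.1 × 0.223 = 0.184, and exp(0.184) = 1.20.
- Same sizes, with BMI and sex reversed: 0.102 − 0.059 − 0.022 = 0.02, a ratio of about 1.02.

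Simulation of 30 v 70 with a true ratio of 1, exponential discharge times and censoring at Day 35 agrees. With these effects (800 trials per scenario, about 84–86 discharges), the short and full models gave 1.02/1.02 when balanced. They gave 1.06/0.99, 1.13/1.00 and 1.20/1.01 across imbalances of 10–20 points in comorbidity, 0.1–0.3 SD in BMI and 0–10 points in sex. A second set (400 trials, about 90 discharges; effects 0.7, 0.85 and 0.8) gave 0.99/1.00 when balanced. It gave 1.09/0.99 at 10 points in sex and comorbidity with 0.2 SD in BMI, and 1.20/1.00 at 20 points with 0.4 SD.

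**6. Price of the longer list.** In the second set the standard deviation of the log hazard ratio rose from 0.250 to 0.265, 0.246 to 0.265 and 0.261 to 0.285, that is by 6–9%.

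**7. Scale against imprecision.** With 85 discharges split 30:70, SE ≈ 1/√(85 × 0.3 × 0.7) = 0.24, so the 95% limits lie a factor of about 1.6 either side. Ratios of 1.06 and 1.20 (logs 0.058 and 0.182) are about 0.25 and 0.77 of that SE.

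**The case against.** The case for leaving the plan alone has real substance.

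- **The omitted variables are partly controlled already.** Gender, BMI and key comorbidity are in the propensity score. The missing caliper makes residual imbalance possible; it does not show that it is likely. This stands.
- **An adjusted analysis of hospital stay exists.** The linear model for length of hospitalisation carries all five covariates. This stands, though that model treats deaths and censoring differently and gives no hazard ratio. Two analyses of nearly the same outcome could then differ through adjustment alone.
- **Secondary endpoints are descriptive and unpowered** (SAP 8.4 and 11.2), and one short prespecified list is a defensible style. This limits the weight of the point, but 8.2 and 11.2 still disagree.

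A reader might also infer more than the documents support:

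- **That the discharge model departs from the protocol's Cox model.** Protocol 11.1.2 has one survival endpoint and treats length of stay as continuous, so the Cox list in Protocol 11.3.3 governs survival, not discharge. The departure from that list concerns the survival model.
- **That the planned test has an inflated false-positive rate or loses power through the short list.** The SAP takes significance from the log-rank test, which does not change with the Cox covariates. Only the hazard ratio and its interval are affected.
- **That discharge events are known to be plentiful.** No document gives a discharge rate; at 50% discharged, the six-parameter model has 8.3 events per parameter.

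**Conclusion.** The inconsistency is exact: SAP 11.2 omits three covariates that SAP 8.2 promises, without a reason, and the SAP's own removal rule does not lead there. For Day-35 survival a short model is sensible with 4–15 deaths expected, but it should be declared. For time to discharge the omission leaves the hazard ratio and confidence interval open to bias from residual imbalance against mostly historical controls.

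The size is uncertain. A spurious ratio of about 1.06 to 1.20 follows only from assumed effects and from imbalances acting in the same direction; with offsetting imbalances it is near 1.0. Even the upper value is smaller than one standard error. This is a low-severity point, worth correcting because the correction costs almost nothing.

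**What to change.** 1. In SAP 11.2, adjust the time-to-discharge Cox model for age, gender, BMI, baseline CRP and key comorbidity, plus treatment, as SAP 8.2 states.
2. Keep the age-and-CRP model for Day-35 survival. Give the reason (few deaths expected), list it as an exception in SAP 8.2, and record it as a departure from the survival Cox model in Protocol 11.3.3. Protocol 11.5 already asks for deviations to be described and justified.
3. Base inference on the discharge comparison on the adjusted hazard ratio and its interval, with the unadjusted log-rank test as supportive.

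The cost is a few lines of SAP text and one changed model statement. All three variables are already in the baseline list of SAP 10.2 and in the propensity score. The statistical price is three more parameters and a standard error about 6–9% larger in the simulations. If far fewer than 60 patients are discharged by Day 35, the existing removal rule still applies. The change does not restore oxygen requirements, which the SAP leaves out of every model; that is a separate matter.
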